10.4 INTERIM ANALYSIS

A DSMB will be established for the study, composed of approximately two to three independent members including physicians knowledgeable in the treatment of PAH and pediatric PAH. Once five subjects have enrolled in Cohort 1 and transitioned from IV/SC Remodulin, the safety data will be reviewed by the DSMB. The IV/SC Remodulin dose will be between 25-75 ng/kg/min, inclusive, for the first five subjects enrolled in Cohort 1. Following the DSMB safety review, the dose range may be expanded to 25-125 ng/kg/min, inclusive, for the remaining subjects.

Additionally, if two or more of the first five subjects within any cohort meet the pre-specified stopping criteria, the data from that cohort will be reviewed prior to enrolling additional subjects into that cohort.

Analysis of pharmacokinetic samples may be performed, as warranted, to guide dosing.

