	All subjects must be optimally treated (as determined by the Investigator) with background PAH therapies (e.g., phosphodiesterase type 5 inhibitor [PDE-5i], endothelin receptor antagonist [ERA], soluble guanylate cyclase [sGC]) for at least 90 days and have been on a stable dose without changes (except documented weight based adjustments) for at least 30 days prior to the first dose of oral treprostinil.
	 Cohort 1: Remodulin to Oral Treprostinil Transition Subjects must have been receiving IV/SC Remodulin for at least 90 days and at a stable dose for at least 30 days prior to the first dose of oral treprostinil. The IV/SC Remodulin dose will be between 25-75 ng/kg/min, inclusive, for the first five subjects enrolled in Cohort 1. Following a safety review by the Data Safety Monitoring Board (DSMB) after the first five Cohort 1 subjects have been enrolled and transitioned to oral treprostinil (study drug), the dose range may be expanded to 25-125 ng/kg/min, inclusive, for the remaining subjects.
	Cohort 2: Inhaled Prostacyclin to Oral Treprostinil Transition Subjects must have been receiving inhaled prostacyclin therapy for at least 90 days and at a stable dose for at least 30 days prior to the first dose of oral treprostinil.
	Cohort 3: Add-On to Current PAH Therapy in De Novo Prostacyclin Subjects must weigh at least 22 kg.

Drug Dosage and	All Cohorts:
Formulation	All subjects will receive study drug (oral treprostinil extended release tablets). The tablets may be provided as 0.125, 0.25, 1, or
	2.5 mg strengths. Oral treprostinil will be dosed three times daily (TID) or four times daily (QID) at the discretion of the Investigator, with food. Dosing will take place approximately every 6 to 8 hours for TID dosing, or approximately every 4 to 6 hours for QID dosing, with adjustments permitted based on the subject's lifestyle and schedule. Sudden dose escalation or reductions should be avoided as they may lead to intolerable adverse events (AEs) or worsening of PAH. Gradual dose titrations are recommended to reduce the risk to subjects.

Cohort 1: IV/SC Remodulin to Oral Treprostinil Transition

Dose Transition Schedule:

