Following completion of Baseline assessments, the first dose of 0.125 mg oral treprostinil should be taken at the study site. Dosing of oral treprostinil will be initiated at 0.125 mg TID or QID at the discretion of the investigator, with food. Dosing will take place approximately every 6 to 8 hours for TID dosing, or approximately every 4 to 6 hours for QID dosing, with adjustments permitted based on the subject's lifestyle and schedule. Dose changes should be conducted under appropriate medical supervision in consultation with the study site.

Dose Optimization/Evaluation Phase (All Cohorts):

Week 3, Week 6, and Week 12: Subjects will return to clinic for the following assessments: vital signs, six-minute walk test (6MWT)/Borg dyspnea score, Panama and WHO functional classification, symptoms of PAH, and safety assessments. At each visit, females of childbearing potential will undergo a urine pregnancy test. At Week 12, QOL (as measured by PedsQL) and clinical laboratory assessments, including NT-pro-BNP, will occur.

Week 24 (or premature termination): Subjects will return to the clinic for the following assessments: vital signs, physical examination, 6MWT/Borg dyspnea score, CPET, Panama and WHO functional classification, symptoms of PAH, QOL assessment, NT-Pro BNP, cMRI, clinical laboratory assessments, electrocardiogram (ECG), and safety assessments. Females of child bearing potential will undergo a urine pregnancy test. In addition all subjects will undergo an 8-hour PK assessment.

Once the first five subjects have enrolled in Cohort 1 and transitioned from IV/SC Remodulin, the safety data will be reviewed by a Data Safety Monitoring Board (DSMB). The IV/SC Remodulin dose will be between 25-75 ng/kg/min, inclusive, for the first five subjects enrolled in the cohort. The dose range may be expanded to 25-125 ng/kg/min, inclusive, for the remaining subjects following the safety review.

Additionally, if two or more of the first five subjects within any cohort meet the pre-specified stopping criteria (see Section 5.4) the data from that cohort will be reviewed by the DSMB

prior to enrolling additional subjects into that cohort. If any of these events happen after the first four weeks of the study, it is not required that a subject be removed from the study. The Investigator will determine whether it is safe for a subject to remain in the study.

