^a The Screening phase can begin up to 28 days prior to Baseline. Baseline assessments can be conducted over five days (120 hours) prior to the first dose of oral treprostinil, to allow for scheduling of all activities. Screening and Baseline visits may be combined if all assessments are completed and entry criteria are satisfied within five days (120 hours) prior to first dose of oral treprostinil. Baseline PK assessments for subjects enrolled in Cohort 1 can be performed up to seven days prior to beginning oral treprostinil. The subject will begin transitioning from IV/SC Remodulin to oral treprostinil in the hospital (Week 0).

- ^b The window for Week 3, 6, 12, and 24 visits is \pm five days.
- ^c The Week 24/Premature Termination visit can occur over five days (120 hours) to allow for scheduling of assessments on separate days; however, no oral treprostinil dose adjustments are allowed from five days prior to the Week 24 study visit until all Week 24/Premature Termination procedures have been completed, unless required to protect subject safety. If the subject discontinues the study before Week 24, then the Premature Termination visit should be conducted. All assessments should be conducted prior to discontinuation of oral treprostinil or as close as possible to the last dose of study drug.
- ^d PedsQL questionnaires must be completed based upon the subject's age group and in accordance with the questionnaire administration guidelines. Must be completed as the first assessment at Baseline (or as part of the Screening visit assessment [after informed consent is obtained] if the Screening and Baseline visits are combined), Week 12 and Week 24 /Premature Termination, before the respondents complete any other health data forms, and before they see their physician/healthcare provider or have other assessments performed.
- ^e Vital signs must be collected after five minutes of rest (sitting); no other measurements or procedures should be performed during this five-minute period. All vital signs will be collected prior to or after at least 30 minutes following the 6MWT.
- ^f Blood for NT-pro-BNP assessment must be drawn prior to conducting the 6MWT or CPET and will occur prior to the first dose of oral treprostinil at Baseline (or as part of the Screening visit assessment if the Screening and Baseline visits are combined).

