4.1 INCLUSION CRITERIA

A subject is eligible for inclusion in this study if all of the following criteria apply:

- 1. Legal guardian informed consent and subject assent, if appropriate, to participate in the study is voluntarily given.
- 2. The subject is between 7 and 17 years of age, inclusive, on the date informed consent is signed.
- 3. *Cohort 3:* The subject must weigh a minimum of 22 kg at Screening.
- 4. The subject has a current diagnosis of PAH (WHO Group I) associated with:
 - a. Idiopathic or heritable PAH
 - b. Persistent PAH for at least one year following surgical repair of a congenital systemic-to-pulmonary cardiac shunt, congenital heart disease, or other congenital heart lesions with no clinically significant residual defects and condition is stabilized hemodynamically
 - c. PAH in subjects with unrepaired restricted atrial septal defect, ventricular septal defect, or patent ductus arteriosus; subject must have a resting postductal oxygen saturation (off oxygen) of greater than 88%
- The subject has a current diagnosis of PAH confirmed by right heart catheterization (RHC) prior to the Screening visit with the following parameters:
 - a. Mean pulmonary arterial pressure (mPAP) of ≥25 mmHg
 - b. Pulmonary vascular resistance index (PVRi) of >3 Wood Units * m²
 - c. Left ventricular end diastolic pressure (LVEDP) or pulmonary capillary wedge pressure (PCWP) of ≤15 mmHg

- 6. Cohort 1: The subject must have been receiving IV/SC Remodulin for at least 90 days without dose change for at least 30 days prior to Baseline. The IV/SC Remodulin dose will be between 25-75 ng/kg/min, inclusive, for the first five subjects in the cohort. Following a safety review, the dose range may be expanded to 25-125 ng/kg/min, inclusive, for the remaining subjects. Subjects must be receiving stable doses of all other PAH medications for at least 14 days prior to the Baseline assessments; exception for diuretics and anticoagulants as outlined in Section 4.3.1.
- 7. Cohort 2: The subject must have been receiving inhaled prostacyclin for at least 90 days and has been at the current stable dose without changes for at least 30 days prior to Baseline. Subjects must be receiving stable doses of all other PAH medications for at least 14 days prior to the Baseline assessments; exception for diuretics and anticoagulants as outlined in Section 4.3.1.

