5.4 STOPPING CRITERIA

If any of the following events occur within the four weeks following the first dose of drug oral treprostinil given for all cohorts, the subject should be transitioned back to IV/SC Remodulin (Cohort 1 subjects only) or tapered off oral treprostinil, as appropriate, and discontinued from the study:

- Unplanned hospitalization as a result of worsening PAH
- Clinically significant worsening in PAH symptoms or signs, which the Investigator feels requires a change of current therapy.

If two or more of the first five subjects in any cohort meet the stopping criteria, the data will be reviewed by a Data Safety Monitoring Board (DSMB) prior to enrolling additional subjects into that cohort.

If any of these events happen after the first four weeks of the study, it is not required that a subject be removed from the study. The Investigator will determine whether it is safe for a subject to remain in the study.

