6.1.1 Cohort 1: IV/SC Remodulin to Oral Treprostinil Transition

Once all entry criteria have been met and Baseline assessments completed, subjects should begin transition in the hospital from IV/SC Remodulin to oral treprostinil with a goal for complete transition off of IV/SC Remodulin within five days of the start of the transition. If possible, Day 5 (or final day of hospital stay if transition occurred in less than 4 days) of hospital stay should be reserved as an observational period for subjects successfully transitioned to oral treprostinil and no longer receiving IV/SC Remodulin. A cross titration will occur so that the dose of IV/SC Remodulin is decreased as the dose of oral treprostinil is increased. Once subjects have been transitioned off IV/SC Remodulin, the dose of oral treprostinil may continue to be titrated to the appropriate optimal dose for that subject throughout the rest of the study.

Dosing guidelines:

• The following equation can be used to estimate a comparable total daily dose of oral treprostinil (in mg) using the subject's dose of IV/SC Remodulin (in ng/kg/min) and weight (in kg):

Oral treprostinil total daily dose (mg) = 0.0072 x Remodulin dose (ng/kg/min) x weight

- IV/SC Remodulin should not be decreased more than 30 ng/kg/min within a 24 hour period
- Oral treprostinil should be increased in proportion to Remodulin decreases and the subject's weight
- IV/SC Remodulin doses should be adjusted (i.e., decreased) at the same time oral treprostinil dose is increased

Hospital Day	IV/SC Remodulin (ng/kg/min)	Oral Treprostinil (mg)		
Day 1 (0-24 hours)	Day 1 (0-24 hours)			
Morning (upon admission)	65	0		
Midday	59	0.5		
Evening	53	1		
Day 2 (24-48 hours)				
Morning	47	1.5		
Midday	41	2		
Evening	35	2.5		
Day 3 (48-72 hours)				
Morning	29	3		
Midday	23	3.5		
Evening	17	4.		
Day 4 (72-96 hours)				
Morning	11	4.5		
Midday	5	5		
Evening	0	5.5 (target dose)		
Day 5 (96-120 hours): Observational period prior to hospital discharge				
Morning	0	continue to titrate if appropriate		
Midday	0	continue to titrate if appropriate		
Evening	0	continue to titrate if appropriate		

Example TID Dosing Schedule for a 35 kg Subject:

Hospital Day	IV/SC Remodulin (ng/kg/min)	Oral Treprostinil (mg)	
Day 1 (0-24 hours)			
Morning (upon admission)	65	0	
Midday	61	0.25	
Early Evening (PM #1)	57	0.5	
Late Evening (PM #2)	53	0.75	
Day 2 (24-48 hours)			
Morning	48	1.125	
Midday	44	1.375	
Early Evening (PM#1)	40	1.625	
Late Evening (PM #2)	36	1.875	

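### The DSMB review that may open Cohort 1 to Remodulin doses up to 125 ng/kg/min is triggered by five completed transitions, with no minimum follow-up stated in the protocol or SAP

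*Protocol*

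**What the plan says.** The trigger appears in four places in nearly the same form. Protocol Section 10.4: "Once five subjects have enrolled in Cohort 1 and transitioned from IV/SC Remodulin, the safety data will be reviewed by the DSMB". Protocol Section 3.1: "Once the first five subjects have enrolled in Cohort 1 and transitioned from IV/SC Remodulin", followed by review of the safety data. The synopsis, under Cohort 1 eligibility: "after the first five Cohort 1 subjects have been enrolled and transitioned to oral treprostinil (study drug), the dose range may be expanded". SAP Section 5 repeats the condition and adds that the data will be prepared under a separate DSMB analysis plan. Inclusion criterion 6 (Section 4.1) is looser: "Following a safety review, the dose range may be expanded to 25-125 ng/kg/min, inclusive, for the remaining subjects".

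Section 6.1.1 sets the pace of transition, "with a goal for complete transition off of IV/SC Remodulin within five days of the start of the transition", and foresees a faster one: "or final day of hospital stay if transition occurred in less than 4 days". Its only rate limit is a maximum Remodulin decrease of 30 ng/kg/min in 24 hours. A transition may also take up to four weeks (Section 3.1).

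The stopping rule in Section 5.4 uses a longer clock: "If any of the following events occur within the four weeks following the first dose of drug oral treprostinil given for all cohorts". The events are unplanned hospitalization for worsening PAH, and clinically significant worsening that the investigator judges to need a change of therapy. Two or more such subjects among the first five in a cohort bring a DSMB review before further enrolment in that cohort.

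**The concern.** The protocol treats the first four weeks on oral drug as the period in which worsening PAH requires a child to leave the study. The decision to admit children on higher infused doses does not use that period. It is tied to completion of transition, which is planned to take days. The review may therefore be held before the most recent child has passed most of the four-week window.

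That child would have had only the inpatient assessments of Days 2-5. Section 7.4.1 does not require vital signs, PAH symptoms or the walk test after Day 5, even if the stay is longer, and it lists no functional class. The next scheduled set, with the first functional class after Baseline, is the Week 3 visit. At stake is a decision to raise the entry ceiling for children by 50 ng/kg/min on incomplete early safety data.

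**Working it through.** The documents state no follow-up figure for this review, so there is none to reproduce.

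**Inputs from the documents.** Stopping window: 4 weeks = 28 days from the first oral dose (Section 5.4). Target: off Remodulin within 5 days; both worked examples reach zero on Day 4 (Section 6.1.1). Limit: 30 ng/kg/min per 24 hours. First-five entry doses: 25-75 ng/kg/min. Week 3 visit: Day 22 (Table 3-1); "The window for Week 3, 6, 12, and 24 visits is" five days either side, so Day 17-27.

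**Step 1: the last child at the moment of transition.** Share observed = days since first oral dose / 28.
- Target pace: 4/28 = 14.3%; 5/28 = 17.9%.
- Fastest under the daily limit, dose/30 rounded up: up to 30 ng/kg/min, 1 day (1/28 = 3.6%); above 30 to 60, 2 days (7.1%); above 60 to 75, 3 days (10.7%).

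All of these fall before Day 17, so the Week 3 visit has not taken place.

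**Step 2: effect of a lag before the data cut.** Share = min(28, d + lag)/28, where d is the day off Remodulin. The lag is not stated, so a range is shown.

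| Lag (days) | 0 | 7 | 14 | 23 |
|---|---|---|---|---|
| d = 5 | 18% | 43% | 68% | 100% |
| d = 4 | 14% | 39% | 64% | 96% |

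**Step 3: what could be missed.** Assumptions, none from the documents: children independent; risk p of a stopping event within 28 days; entries s days apart; every child's time counted from the first dose, with the fifth off Remodulin on Day 5. The calculation does not condition on earlier status. Observed days are t_k = min(28, 5 + lag + s·k), k = 0 to 4, counting back from the last child. With constant hazard, F(t) = 1 − (1 − p)^(t/28).

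- At least one in-window event after the cut = 1 − product over children of [1 − (F(28) − F(t_k))].
- 2-of-5 threshold first reached after the cut = P(at least 2 by Day 28) − P(at least 2 by the cut).

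Example, p = 0.2, s = 14, lag 0: observed days are 5, 19, 28, 28, 28. F(5) = 0.0391 and F(19) = 0.1405, so the late probabilities are 0.1609 and 0.0595. The first quantity is 1 − 0.8391 × 0.9405 = 0.211. The second is 26.3% − 17.4% = 8.9%.

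| Setting | Lag 0 | 7 | 14 | 23 |
|---|---|---|---|---|
| Any late event, p = 0.2, s = 14 | 21% | 12% | 6% | 0% |
| Same, front-loaded hazard* | 13% | 7% | 4% | 0% |
| Same, constant hazard, s = 30 | 16% | 11% | 6% | 0% |
| p = 0.1, s = 14 | 11% | 6% | 3% | 0% |
| p = 0.4, s = 14 | 39% | 22% | 11% | 0% |
| 2-of-5 first reached late, p = 0.2, s = 14 | 8.9% | 5.0% | 2.4% | 0% |
| Same, front-loaded hazard* | 5.3% | 3.0% | 1.5% | 0% |

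*Half the cumulative hazard over Days 0-5, half over Days 5-28.

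**The case against.** The strongest reply is that the cut may exist elsewhere. SAP Section 5 sends data preparation to a separate DSMB analysis plan, a normal home for such a rule. A reader might infer from the protocol and SAP that no minimum exists at all. The documents do not support that; they show only that none is stated in these two texts.

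A reader might also infer that the board will decide on 4-5 days of data. That does not follow. Only the last child is that early, earlier children will usually have more follow-up, and any time spent preparing data and convening narrows the gap. Expansion is optional, and an independent board can ask for more. Entry spacing may also be longer than 14 days. From the original protocol (29 July 2014) to the final SAP (15 August 2017) is 1,113 days, and 1,113/40 planned subjects is about 28 days per subject across cohorts. This is a rough guide only, as accrual is not reported. At such spacing only the last child is incomplete.

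Nor would late events go unseen. Unplanned hospitalizations are SAEs (Section 9.1.4), reported to the sponsor within 24 hours (Section 9.4). Weekday contact covers the first two weeks (Section 3.3.2.6). The inpatient days are densely assessed, and nothing ends the 2-of-5 rule at the expansion review. These points stand and reduce the size of the problem. They do not supply a minimum. A single late event would not trigger the 2-of-5 rule, yet it bears on whether to raise the ceiling.

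Finally, it might be argued that transition here means the primary endpoint, which requires Week 4 status and maintenance to Week 24. The trigger does not refer to that endpoint, and Section 6.1.1 describes children still in hospital as successfully transitioned.

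**Conclusion.** The point holds in a limited form. The protocol and SAP let the dose-range review go ahead once five children have transitioned, without requiring that the protocol's own four-week stopping window has been observed. For the last child, 14-18% of the window is what the target schedule gives; it is not the permitted minimum, which is 1-3 days (4-11%) under the daily limit.

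The consequence depends on how soon the board meets. In the central illustration, the chance of any in-window event after the cut falls from 21% to 6% as the lag goes from 0 to 14 days. For the protocol's own 2-of-5 threshold it falls from about 9% to 2%. Both reach zero at 23 days. Risk, spacing, hazard shape and lag are all assumed. Confidence is medium, mainly because the DSMB analysis plan was not available. The change is worth making because it is cheap and concerns a dose-range decision in children.

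**What to change.** In the synopsis, Protocol Sections 3.1 and 10.4, and SAP Section 5, state:

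> The DSMB will review safety data from all Cohort 1 subjects dosed to date, including failed transitions and withdrawals, once five subjects have transitioned off IV/SC Remodulin and each of these five has either completed 28 days from the first oral dose or met a Section 5.4 stopping criterion. A subject who leaves earlier for another reason is reviewed and is replaced in the count.

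In the same places and in inclusion criterion 6, replace the wording that ties the lower range to the first five subjects with:

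> The entry range is 25-75 ng/kg/min until the DSMB review described in Section 10.4 is complete.

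Without this second change, the replacement rule would conflict with the first-five wording. If the DSMB analysis plan already sets a cut, align the text with it. The 28-day cut also takes in the whole Week 3 visit window.

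One limit remains. For a slow transition, 28 days from the first oral dose covers the stopping window but may leave little time off infusion. The board should be shown days off Remodulin for each child.

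Cost: one paragraph in four places, the range wording there and in criterion 6, and a check of the DSMB plan. Expansion could come about 23-27 days later (28 − 5 to 28 − 1), plus any wait for a replacement, and less if the board would meet later anyway. Enrolment at 25-75 ng/kg/min continues meanwhile.

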10.5 OTHER ANALYSES

Additional exploratory analyses may be conducted based on available study data.

10.6 DATA LISTINGS AND SUMMARIES

The Safety population will be used for all data listings, summaries and figures. All available data will be presented with no imputation for any missing data. Subjects will contribute the data available up to the point of study completion, or study discontinuation for any reason.

In general, listings will be sorted by subject, descriptive summaries will include number of observations (n), mean, standard deviation (SD), median, minimum, maximum for continuous variables and n and percent for categorical variables. For all continuous variable summaries, n, arithmetic mean, median, minimum, maximum, SD, % coefficient of variation (CV), and 95% confidence interval (CI) for the arithmetic mean will be provided.

Plasma concentration data and derived pharmacokinetic parameters will be summarized and displayed in both tabular and graphical form. Noncompartmental analysis of concentration time data will be performed using WinNonlin. Comparative plots of individual concentration data will be produced separately for each cohort as well as summaries across subjects.

